Summarize in 2-3 paragraphs past experimental and/or clinical findings leading to the design of this protocol. Include any relevant past or current research by the PI. For drug and device studies, summarize the previous results (i.e., Phase I/II or III studies).

For millennia, people have listened to and enjoyed music for entertainment, as a distraction from daily troubles, and as a means to relax and relieve stress. It is no real surprise that the relaxing and stress-relieving effects of music have been shown in patients having surgery. For patients having surgery with spinal anesthesia, music therapy during the operation decreases sedation requirements, anxiety and may improve patient satisfaction. 1, 2, 3, 4, 5, 6, 7 Music therapy during surgery may also lead to a decreased stress response, as evidenced by more stable cortisol levels. 8 Studies done previously have included patients undergoing various surgical procedures, however no studies have been done specifically for patients undergoing total knee arthroplasty. Because total knee arthroplasty is a common procedure usually done under spinal anesthesia at our institution, we would like to study the effects music therapy could have on our patient population.

16. Participants (Screening and Selection)

a. How many participants are to be enrolled at UAB (if other sites relying on UAB IRB, list the number for each site)? $\underline{100}$

If multi-site study, total number at all sites/institutions:

b. Describe the characteristics of anticipated or planned participants (if multiple groups, repeat list for each group).

Sex: M,F

Race/Ethnicity: any Age: ≥18 years

Health status: ASA Physical Status I, II, III

c. From what population(s) will the participants be derived? The study population will be derived from those patients scheduled for total knee arthroplasty

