Statistical Power and Sample Size Estimates (if applicable): Sample size (100) was determined using a Cohen's d table assuming a mean STAI anxiety score of 35 (SD = 10) on a scale of 20-80 for control subjects. A difference of STAI score of 5 between two study groups will be clinically relevant. A sample of 50 participants (25 patients per group) will have approximately 85% power to detect a reduction in anxiety score difference of 5 with significance level alpha of 0.05.

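### The stated 85% power does not follow from the plan's own inputs: a two-sided t-test has about 41% power with 25 per group and about 70% with 50 per group, and one paragraph gives two totals, 100 and 50

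*Combined protocol and SAP*

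**What the plan says.** The only sample-size justification is the paragraph on statistical power and sample size at the end of the Statistical Considerations. It opens with one total: "Sample size (100) was determined using a Cohen's d table". It gives the distributional input as "assuming a mean STAI anxiety score of 35 (SD = 10) on a scale of 20-80 for control subjects", and takes a 5-point difference between the two groups as clinically relevant. It then attaches the power to a different total: "A sample of 50 participants (25 patients per group) will have approximately 85% power to detect a reduction in anxiety score difference of 5", at alpha 0.05.

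Item 16.a of the protocol, which asks "How many participants are to be enrolled at UAB", is answered with 100. Items 16.e and 17 give 1:1 randomisation. The Primary Outcome Analysis paragraph names Student's t-test. The documents do not state whether the test is one- or two-sided, give no correlation between preoperative and postoperative scores, make no allowance for losses, and do not explain how 50 relates to 100.

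**The concern.** A standardised difference of 0.5 is a moderate effect, and 25 per group is far too few to detect it with 85% power. The total of 100 also falls short, so the problem is more than a slip between the total and the number per group.

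Two consequences follow:

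- If recruitment ended at 50 because the paragraph presents 50 as enough, a true 5-point effect would be missed more often than found.
- If all 100 are enrolled, a null anxiety result would be read as coming from a trial with a 15% chance of missing a 5-point effect, when that chance is about 30%.

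**Working it through.** **Inputs.** From the sample-size paragraph: SD 10, difference 5, alpha 0.05, and either 50 in total (25 per group) or 100 in total. From Items 16.e and 17: 1:1 allocation, so 100 means 50 per group. From the Primary Outcome Analysis paragraph: Student's t-test. Assumption: a two-sided test, because sidedness is not stated; one-sided values are shown as well.

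**Formula.** Standardised difference d = 5/10 = 0.5. For n per group, the t statistic has 2n − 2 degrees of freedom and noncentrality λ = d·√(n/2). Power is the probability that this noncentral t exceeds the critical value.

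**Attempt to reproduce the plan's 85% with 25 per group.** λ = 0.5 × √12.5 = 1.768, with 48 degrees of freedom and a two-sided critical value of 2.011. Power = 41.0%. The normal approximation gives Φ(1.768 − 1.960) = 42.4%, so the choice of method does not explain the gap. One-sided power is 53.9%. The 85% is not reproduced.

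**If 50 per group was meant.** λ = 0.5 × √25 = 2.5, with 98 degrees of freedom and a critical value of 1.984. Power = 69.7% two-sided (70.5% by normal approximation) and 79.9% one-sided.

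| Reading of the sample size | Two-sided | One-sided |
|---|---|---|
| 25 per group (50 total) | 41.0% | 53.9% |
| 50 per group (100 total) | 69.7% | 79.9% |
| 100 per group (200 total, contradicts Item 16.a) | 94.0% | 97.0% |
| Paired or one-sample test, d = 0.5, n = 25 | 67.0% | 78.3% |
| Paired or one-sample test, d = 0.5, n = 50 | 93.4% | 96.7% |

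No row is within 2 points of 85%. The paired rows would also not test the between-group difference that the paragraph calls relevant.

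**Sample size needed for 85%.** By normal approximation, n = 2(1.960 + 1.036)²/0.5² = 71.8, so 72 per group. The t-test solution is 72.8, so 73 per group and 146 in total. One-sided, it is 58.2, so 59 per group.

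**What the two totals can detect at 85% power (two-sided t).**

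- 25 per group: d = 0.865, which is 8.65 points at SD 10. For 5 points, the SD would have to be 5/0.865 = 5.8.
- 50 per group: d = 0.605, which is 6.05 points at SD 10. For 5 points, the SD would have to be 5/0.605 = 8.3.

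**The case against.** The strongest defence is that the SD of 10 may not be the SD of the quantity analysed. The analysis paragraph compares preoperative with postoperative scores, and the power sentence speaks of a reduction in a score difference, so a change score or a baseline-adjusted comparison could be meant. Its variance depends on the pre-post correlation r:

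- **25 per group:** at r = 0.8, a change-score t-test has 78.2% power two-sided and 86.7% one-sided; baseline adjustment gives 82.3% two-sided.
- **50 per group:** at r = 0.6, a change-score test has 79.0% two-sided and 87.1% one-sided; baseline adjustment gives 87.2% two-sided.

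Some combination can therefore reach 85%. But the plan states no correlation, names no adjusted analysis, gives the SD for the score itself and cites a Cohen's d table. An unstated assumption cannot support the stated figure. What stands is that the conclusion holds under the stated inputs, not under every conceivable endpoint.

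Two further points are fair. Item 16.a and the opening of the paragraph both say 100, and nothing sets a stopping point at 50, so the likelier practical exposure is 70% rather than 41%. Also, 70% assumes that 50 per group are analysed. Item 17.G excludes failed spinals, Item 20.b removes patients who cannot tolerate headphones, and no loss rate is given. As an illustration, 45 analysed per group gives 65.0% and 40 gives 59.8%, two-sided. This makes 70% an upper figure; it does not help the 85%.

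**Conclusion.** The concern holds. With d = 0.5, a two-sample t-test and two-sided alpha 0.05, power is 41.0% for the sample that the sentence names, 44 percentage points below the claim. It is 69.7% for the planned enrolment, about 15 points below. One-sided testing (53.9% and 79.9%) does not close the gap. Separately, the paragraph gives totals of 100 and 50 that nothing in the documents reconciles; Item 16.a supports 100.

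The figures rest on SD 10 applying to the analysed score, equal groups and no losses. This must be corrected, because it is the trial's only sample-size justification and its own inputs contradict it.

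**What to change.** Delete the sentence about 50 participants and state 100 as the single enrolment target. Replacement text could read: *With 100 participants (50 analysed per group), an SD of 10 and a two-sided alpha of 0.05, the trial has about 70% power for a 5-point difference between groups and 85% power for a difference of 6.1 points.* State which STAI quantity is compared, and add an expected loss rate or a short range of analysed numbers.

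If the team adopts a baseline-adjusted analysis, it should state the power with its assumed correlation. With 50 per group and a two-sided test, r = 0.5 gives about 82% for 5 points, and r of about 0.56 is needed for 85%. This is optional and not part of correcting the error.

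The cost is SAP wording and a less favourable power statement; no extra patients are required. If the sponsor wants to keep 85% power for 5 points with the unadjusted two-sided test, the price is 146 analysed participants, 46 more than planned. That choice is the sponsor's.
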